2.4.4 Epithelial-mesenchymal transition (EMT)

EMT is a dynamic process that leads to increases in the migratory and invasive properties of tumor cells (1). Histologically, these changes involve the loss of epithelial marker E-cadherin (E) and gain of the mesenchymal marker intermediate filament vimentin (V); loss of E-cadherin is linked to poor prognosis, tumor progression, and metastasis^{26,27}.

Recent data from DCTD confirm the existence of "transitional" cells that co-express both E-cadherin and vimentin at the cellular level in FFPE clinical biopsies. Quantitative analysis of various histologies using an immunofluorescence assay developed and validated by DCTD revealed all possible phenotypes from very epithelial (E+V- colorectal carcinoma), mesenchymal (E-V+ sarcomas), heterogeneous mixtures of E+V- and E-V+ subpopulations, and EMT.

The potential clinical utility of this assay has been demonstrated: treatment with the multikinase inhibitor pazopanib resulted in a significant shift towards the mesenchymal phenotype in drug-sensitive but not insensitive human xenograft models (manuscript in preparation). The EMT immunoassay will be used as to elucidate "baseline" EMT status in study patients—differences observed to date suggest inter-patient phenotypic variation to be as significant a factor as histological differences within carcinomas—as well as to characterize drug response.

2.4.5 Potential predictive molecular biomarkers of AZD1775 antitumor activity

Tumors containing molecular alterations that enhance replicative stress may be particularly susceptible to Wee1 inhibition by AZD1775, with the heightened cell cycle stress in the presence of both factors representing a synthetic lethal interaction. Several genomic alterations that induce replicative stress have been shown to potentially enhance AZD1775 antitumor activity in preclinical and/or clinical studies; these alterations include loss of function mutations in *BRCA1/2*^{16,28,29} and *SETD2*³⁰ and amplification of *CCNE1* or *MYC*²⁹. For active Expansion Arm B patients enrolled at the time of Amendment P (11/2/17) approval or thereafter, tumor biopsy cores remaining after completion of PD biomarker analyses will be used for whole-exome and RNA sequencing to identify these and other mutations or gene expression patterns in patient tumor tissue and to examine potential associations between such molecular alterations and AZD1775 antitumor activity.

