> Weel has additionally been shown to modulate the activity of the Mus81-Emel endonuclease complex responsible for cleavage of stalled replication forks by introduction of double stranded breaks to allow for replication recovery¹³. Massive induction of DNA breaks eventually overwhelms cellular capacity to repair the lesions, and as Weel inhibition also results in abrogation of the G2 checkpoint, cells are pushed towards mitotic lethality secondary to inability to repair damaged DNA. Based on these recent data demonstrating the role of Weel in maintenance of genomic integrity, we propose that AZD1775 may have single agent activity.

15

Non-Clinical Pharmacokinetics

Metabolism

Non-clinical toxicology

At the time of Amendment G, dated 07/17/2014, 18 patients have been enrolled onto Arm A of this study and the MTD established at 225 mg twice daily for 5 doses each week, for two consecutive weeks¹⁶. Confirmed partial responses were observed in two patients carrying BRCA mutations: one with head and neck cancer and one with ovarian cancer. As of Amendment I (dated 8/6/15), a total of 10 patients have been accrued to Arm B (qd dosing); this schedule has been well tolerated to date but persistent grade 2 nausea and vomiting on DL2 necessitated expansion to 6 patients to better define the toxicity. At the time of Amendment M (dated 11/20/16), a total of 24 patients have been accrued to Arm B, and we have established the Arm B MTD as DL4 (300 mg once daily on days 1-5 each week for two weeks).

Clinical Efficacy

Of 176 evaluable patients who received AZD1775 (either single or multiple doses) as monotherapy or in combination with gemcitabine, cisplatin, or carboplatin on Study PN001, a partial response (PR) (confirmed and unconfirmed) was observed in 17 (9.7%) patients, and stable disease (SD) was observed in 94 (53.4%) patients¹⁷. A phase II trial of AZD1775 in combination with carboplatin in patients with refractory or resistant TP53-mutated ovarian cancer (Study PN009) has also been performed, yielding a 43% overall response rate (partial response + complete response)¹⁸.

Safety

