2.5 Genetic Sequencing Research Ethics

This trial will collect genetic data from active Expansion Arm B patients, enrolled at the time of Amendment P (11/2/17) approval or thereafter, for exploratory studies to examine potential associations between genomic and RNA expression alterations and AZD1775 antitumor activity. Tissue specimens used for sequencing analyses will be de-identified, with only limited clinical annotation (e.g., response to AZD1775) maintained for each specimen. Designing the study poses challenging questions about informed consent, the privacy of the patient and the patient's family, the researchers' obligation to disclose genetic information to the patient, and the use and storage of research data³¹⁻³³. In the vast majority of cases, we do not know the medical significance of genetic variants^{34,35}. These challenges will continue to be evaluated to maintain the rigor and integrity of the study and the wellbeing of our patients. A Certificate of Confidentiality has been obtained from the NIH to help protect the privacy of all study participants.

The protocol includes a separate informed consent form for active Expansion Arm B patients enrolled at the time of Amendment P (11/2/17) approval or thereafter; this consent form contains language pertaining to genetic sequencing studies. Active Expansion Arm B patients already enrolled at the time of Amendment P approval will be re-consented to the

new, "genetic analysis" consent form prior to use of their specimens for exploratory sequencing analyses.

Whole-exome sequencing (performed for research purposes but non-CLIA) of tumor and blood can detect non-ambiguous germline variants, which may raise health and privacy implications for the patient and his or her family. WES will not be validated for clinical use, and no clinical decisions can be made based on its results. Furthermore, no genetic data will be shared with the patient.

This study does not meet the criteria specified by the NIH Genomic Data Sharing (GDS) Policy (see Section 12.4), and therefore, a GDS plan has not been included in this protocol.

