9.3 Exploratory whole-exome and RNA sequencing

For active Expansion Arm B patients enrolled at the time of Amendment P (11/2/17) approval or thereafter, baseline, cycle 1 day 8, and progression/"restaging follow-up" tumor biopsy tissue remaining after completion of PD biomarker analyses will be used for exploratory whole-exome sequencing (WES) and RNA sequencing (RNA-seq) as appropriate to identify tumor genomic alterations and gene expression patterns potentially associated with AZD1775 antitumor activity, including loss of function mutations in SETD2³⁰ and amplification or overexpression of CCNE1 or MYC²⁹. Baseline and cycle 1 day 8 blood samples will also be collected for sequencing to enable comparison of tumor and germline sequences. Tissue specimens used for sequencing analyses will be de-identified, with only limited clinical annotation (e.g., response to AZD1775) maintained for each specimen. Active Expansion Arm B patients already enrolled at the time of Amendment P approval will be re-consented to the new, "genetic analysis" consent form prior to use of their specimens for exploratory sequencing, and, if both pre- and post- biopsies have

already been collected from such patients, a blood sample will be collected at time of re-consent for germline DNA analysis, as described below.

Biopsy cores and tissue sections are to be used for exploratory WES or RNA-seq only after PD biomarker analyses have been completed. Tissue availability will be tracked in real time using Labmatrix. Although the MoCha Laboratory is CLIA-certified, these sequencing studies will not be done per CLIA specifications as the data are not returned to the patients or used for clinical decision making. WES analysis will be prioritized over RNA-seq (see "Biopsy specimen use prioritization" diagram, below). WES and RNA-seq analysis of both baseline and cycle 1 day 8 tumor tissue specimens is preferred; however, WES may be performed for a sample from only one time point depending on tissue availability. RNA-seq may be performed for baseline specimens only if no cycle 1 day 8 tissue is available.

Biopsy specimen use prioritization

(1) PD analyses (to fulfill secondary objectives)

(2) WES (baseline and/or C1D8 specimens)

if sufficient tissue remains after (2)

(3) **RNA-seq** (baseline *or* paired baseline and C1D8 specimens)

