13.3 Sample Size/Accrual Rate

With Amendment E (dated 09/24/2013), an additional expansion arm of 6 patients with documented tumors harboring BRCA-1 or-2 mutations will also be enrolled at the MTD to further explore the safety of AZD1775 and obtain preliminary evidence of activity in this patient population. This information may inform patient selection for further development of this agent.

With Amendment G (dated 07/17/2014) an additional Arm B will be established to further evaluate an alternative once-daily dosing schedule. Patients will be enrolled based on the standard 3+3 design. Once the maximum tolerated daily dosing is established, up to 20 additional patients will be enrolled at this dose to further evaluate PD endpoints. With that number, and a tumor biopsy QA criteria failure rate of 40% with respect to paired (pre- and post-dose) biopsies, we have an 87% likelihood of having at least 10 usable PD samples, and 94% likelihood of having at least 9 usable samples. Biopsy tissue quality will be monitored and accrual will stop once we have obtained 10 usable paired samples.

The study is a standard design using 3 patients per arm, unless DLT is noted, in which

point up to 6 patients may be enrolled in an arm. Up to 30 patients will be enrolled for determination of the MTD. In addition, an additional 6 patients will be enrolled at the MTD to further define the dose and evaluate PD studies at this dose level (Expansion Arm A). To allow for a small number of patients who may not be evaluable, and the addition of Arm B, the accrual ceiling for this trial is set at 72 patients. It is anticipated that 2-3 patients per month may be enrolled onto this study. Depending on the number of patients needed to reach MTD, it is expected that 24-48 months will be required to accrue the number of patients necessary to complete the trial.

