13.4 Analysis of Exploratory Endpoints

We will assess the effect of AZD1775 on DNA damage response based on immunofluorescence analysis of markers of DNA damage, Rad51, pNbs1, and γ H2AX in tumor biopsies, pTyr15-Cdk, and caspase 3 in CTCs as a marker of apoptosis.

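### Does sequencing only the still-active early Expansion Arm B patients, with BRCA1/2 among the named targets, need a change to the plan?

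*Combined protocol and SAP*

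**What the plan says.** Section 2.4.5 limits sequencing by the phrase "For active Expansion Arm B patients enrolled at the time of Amendment P (11/2/17) approval or thereafter", and Sections 2.5 and 9.3 repeat the limit. For those enrolled earlier, Section 9.3 adds: "Active Expansion Arm B patients already enrolled at the time of Amendment P approval will be re-consented" to a genetic consent form before their specimens are used. Sections 5.4 to 5.6 end treatment at progression, among other reasons, and take patients off study about 30 days after the last dose. No section defines *active*.

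Sections 2.5 and 9.3 say specimens are de-identified, "with only limited clinical annotation (e.g., response to AZD1775) maintained for each specimen". Finding alterations associated with antitumor activity is an exploratory objective (Sections 1.3 and 13.1.3). The analysis text in Section 13.4 begins "We will assess the effect of AZD1775 on DNA damage response based on immunofluorescence analysis" and covers pharmacodynamic markers only.

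The background list in Section 2.4.5 starts with BRCA1/2 and goes on to SETD2, CCNE1 and MYC. Section 9.3 gives as examples SETD2 loss of function and "amplification or overexpression of CCNE1 or MYC". The précis and schema restrict Arm B to patients without a documented BRCA mutation.

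On numbers, Section 13.3 allows up to 20 expansion patients, says "accrual will stop once we have obtained 10 usable paired samples", and states: "It is anticipated that 2-3 patients per month may be enrolled onto this study". Section 2.3 reports that at Amendment M "a total of 24 patients have been accrued to Arm B".

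**The concern.** Being active on the amendment date means not yet having progressed or stopped for another reason. That is close to the outcome with which the alterations are to be associated. Part of the sequenced set would consist of patients chosen for staying on treatment, mixed with later patients who were not chosen that way, and no section says how to handle the mixture.

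Three things could go wrong:

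- an activity rate read from the sequenced set would flatter the drug;
- an alteration that truly helps would look more common than it is;
- a true association could look stronger or weaker depending on the measure.

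If enrolment and re-consent dates were not kept, an analyst could not allow for late entry. Separately, a reader of Section 2.4.5 might expect a BRCA1/2 result from an arm that leaves known carriers out.

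**Working it through.** **The plan's own figure.** Section 13.3 assumes 20 patients and 40% biopsy failure. With X binomial (20, 0.6), P(X ≥ 10) = 0.872 and P(X ≥ 9) = 0.943. The stated 87% and 94% reproduce. They concern usable pairs, and no calculation is given for the genomic association.

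**How much of the set is selected.** Inputs from the documents are Amendment G (07/17/2014), M (11/20/16) and P (11/2/17). G to M is 857 days, or 28.16 months, so Arm B's past rate is 24/28.16 = 0.852 per month. M to P is 347 days, or 11.40 months. Assumptions are that the expansion opened at M, time on study is exponential with median 2 to 6 months, and 60% of pairs are usable.

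Simulated accrual with the 10-pair stop gives a mean of 16.3 enrolled, 9.6 before P and 6.7 after. The chance that an early patient is still active at P is (1 − e^(−λm))/(λm), with m = 11.40 and λ = ln 2/median.

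| Median (months) | P(active at P) | × 9.6 | Simulated active | Selected share, active/(active + 6.7) |
|---|---|---|---|---|
| 2 | 0.248 | 2.4 | 2.35 | 0.26 |
| 3 | 0.352 | 3.4 | 3.33 | 0.33 |
| 4 | 0.436 | 4.2 | 4.16 | 0.38 |
| 6 | 0.556 | 5.3 | 5.31 | 0.44 |

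The set is then 2.35 + 6.7 = 9 to 5.31 + 6.7 = 12 patients. At the planned 2 to 3 per month, 82 to 100% of the set is selected, but it holds only about 1 to 8 patients.

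**Effect with no true association.** The simulated odds ratio for remaining on study beyond 84 days is 0.99 to 1.01, so the filter produces no false signal.

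**Effect on response, the only outcome named for the specimens.** Suppose selection depends on response alone, with probability s₁ for responders and s₀ for non-responders. The odds ratio becomes (a·s₁ × d·s₀)/(b·s₀ × c·s₁) = ad/bc, which is unchanged. The response rate does move. Assume medians of 2 to 4 months for non-responders and 6 to 12 for responders. A true 10% among early patients then appears as between 0.1×0.556/(0.1×0.556 + 0.9×0.436) = 12% and 0.1×0.733/(0.1×0.733 + 0.9×0.248) = 25%.

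**Effect on a true time-based association.** Assume a hazard ratio of 0.50 and 30% prevalence. In the whole sequenced set at 0.852 per month, prevalence is 33 to 34% and the Cox hazard ratio counted from enrolment is 0.453 to 0.490. The largest bias on the log scale is |ln(0.453/0.50)| = 0.099.

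If every event is observed (the best case), SE(log HR) = √(1/(0.3n) + 1/(0.7n)) = √(1/(0.21n)). This is 0.73 at n = 9 and 0.63 at n = 12. The bias is therefore at most 0.099/0.63 = 0.16 of a standard error. At n = 10 the SE is 0.69, and a 95% interval around 0.50 runs from 0.50×e^(−1.96×0.69) = 0.13 to 0.50×e^(1.96×0.69) = 1.9. At n = 8, the upper end under planned accrual, the SE is 0.77.

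**BRCA1/2.** Assume 1 to 10% undocumented carriers. Twenty patients then yield 0.2 to 2.0 carriers and ten yield 0.1 to 1.0. With one carrier, the smallest possible two-sided Fisher p is 0.05 (n = 20) or 0.10 (n = 10). Any other alteration that rare is as hard to test, so the limit is sample size as much as the arm's entry rule.

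**The case for a change.** The best case for a change is that associating alterations with activity is a stated objective without a line of analysis, while the filter acts on something close to that activity. Within the active-at-P patients alone the distortion is visible. Under the assumed hazard ratio of 0.50, prevalence rises from 30% to 36 to 43%. At a 3-month median, the risk difference for remaining beyond 84 days falls from 0.20 to 0.09 while the odds ratio rises from 2.38 to 2.87. So if an alteration lengthens time on study beyond its effect on response, the odds ratio is not fully protected. Delayed entry at re-consent returns the hazard ratio to 0.50, and the remedy is only wording plus two dates per specimen.

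The selection and the silence stand. The need to amend does not:

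- No section plans a time-based analysis or an activity rate for the sequenced set. The 84-day outcome and the hazard ratio were brought in to test the concern.
- Section 13.5.2 puts the main response analysis on all eligible patients and draws all conclusions from them. Its sentence on sub-analyses is written for exclusions after protocol deviations, but the same principle covers a sequenced subset.
- The annotation wording gives response as an example, not a full list. Specimen labels carry an accession number and collection time (Section 9.2.5), sequencing samples carry patient IDs (Section 9.3.1), and signed consents are kept (Section 14.3). Nothing shows that the dates would be lost.
- Splitting the set gives about 2 to 5 patients against about 7, too few for separate estimates to be informative.
- The list in Section 9.3 is introduced as examples. Only documented BRCA mutations keep a patient out of Arm B, and Section 3.4.1 requires BRCA confirmation only for the BRCA arm. Exome sequencing can still find an undocumented or somatic carrier.

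**Conclusion.** The observation is accurate, but no change to the plan follows. Early patients are selected on time on study because specimens already collected could be used only after re-consent, a reasonable constraint for an objective added late. The consequence is confined to descriptive reading of a small exploratory set. There is no false association under the null, and at the past accrual rate a true hazard ratio of 0.50 shifts by at most about one-sixth of a standard error. If accrual ran at 2 to 3 per month, nearly the whole set would be selected, but with at most about 8 patients no association could be estimated with useful precision.

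These sizes rest on assumptions the documents do not supply: expansion opening at Amendment M, exponential time on study with median 2 to 6 months, a hazard ratio of 0.50 and 30% prevalence. The 0.852 per month comes from the escalation period and may not describe the expansion. Loss of tissue after the pharmacodynamic work was not modelled and would make the set smaller.

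The gap is one a competent analyst fills when reporting: say how many patients enrolled before and after Amendment P were sequenced, show their responses, count time from re-consent if any time-based result is given, and treat BRCA1/2 findings as descriptive. The mismatch between Sections 2.4.5 and 9.3 is a matter of wording and alters no analysis.

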2.5 Genetic Sequencing Research Ethics

This trial will collect genetic data from active Expansion Arm B patients, enrolled at the time of Amendment P (11/2/17) approval or thereafter, for exploratory studies to examine potential associations between genomic and RNA expression alterations and AZD1775 antitumor activity. Tissue specimens used for sequencing analyses will be de-identified, with only limited clinical annotation (e.g., response to AZD1775) maintained for each specimen. Designing the study poses challenging questions about informed consent, the privacy of the patient and the patient's family, the researchers' obligation to disclose genetic information to the patient, and the use and storage of research data³¹⁻³³. In the vast majority of cases, we do not know the medical significance of genetic variants^{34,35}. These challenges will continue to be evaluated to maintain the rigor and integrity of the study and the wellbeing of our patients. A Certificate of Confidentiality has been obtained from the NIH to help protect the privacy of all study participants.

The protocol includes a separate informed consent form for active Expansion Arm B patients enrolled at the time of Amendment P (11/2/17) approval or thereafter; this consent form contains language pertaining to genetic sequencing studies. Active Expansion Arm B patients already enrolled at the time of Amendment P approval will be re-consented to the

new, "genetic analysis" consent form prior to use of their specimens for exploratory sequencing analyses.

Whole-exome sequencing (performed for research purposes but non-CLIA) of tumor and blood can detect non-ambiguous germline variants, which may raise health and privacy implications for the patient and his or her family. WES will not be validated for clinical use, and no clinical decisions can be made based on its results. Furthermore, no genetic data will be shared with the patient.

This study does not meet the criteria specified by the NIH Genomic Data Sharing (GDS) Policy (see Section 12.4), and therefore, a GDS plan has not been included in this protocol.

3 PATIENT SELECTION

3.1 Eligibility Criteria

- **3.1.1** Patients must have histologically confirmed solid tumors for which all standard therapy known to prolong survival have failed or for which standard therapies do not exist.
- **3.1.2** Patients must have measurable disease or evaluable disease for the escalation phase; for the 6 additional patients enrolled at MTD for further evaluation of PK and PD endpoints (Expansion Arm A). For the 6-patient BRCA-mutation expansion arm, patients must have measurable disease; however, tumor biopsies are optional. For Expansion Arm B, patients must have tumor amenable to biopsy (excisional or incision biopsies of skin or H & N lesions under visualization) and willingness to undergo a tumor biopsy *or* patient will be undergoing a procedure due to medical necessity during which the tissue may be collected, *or* tumor biopsy tissue from a previous research study or medical care is available for submission at registration. Criteria for the submission of tissue are:
 - Tissue must have been collected within 3 months prior to registration
 - Patient has not received any intervening therapy for their cancer since the collection of the tumor sample
 - Tumor tissue must meet the minimum requirements outlined in Section 9.
- **3.1.3** Patients must have completed any chemotherapy, radiation therapy, surgery, or biologic therapy \geq 3 weeks (or \geq 5 half-lives, whichever is shorter) prior to entering the study. Patients must be \geq 2 weeks since any prior administration of a study drug in an exploratory IND/Phase 0 study or \geq 1 week from palliative radiation therapy. Patients must have recovered to eligibility levels from prior toxicity or adverse events.
- **3.1.4** Age \geq 18 years of age.
- **3.1.5** ECOG performance status ≤ 1 (Karnofsky >60%, see Appendix A).
- **3.1.6** Life expectancy of greater than 3 months.

3.1.7 Patients must have normal organ and marrow function as defined below:

 leukocytes 	≥3,000/mcL
– absolute neutrophil count	≥1,500/mcL
– platelets	\geq 100,000/mcL
– hemoglobin	>9 g/dL
– total bilirubin	≤ 1.5 X institutional upper limit of normal
- AST(SGOT)/	
– ALT(SGPT)	≤ 3 X institutional upper limit of normal
– creatinine	\leq 1.5X institutional upper limit of normal
	OR
 creatinine clearance 	$>60 \text{ mL/min}/1.73 \text{ m}^2$ for patients with creatinine
	levels above institutional normal.

- **3.1.8** The effects of AZD1775 on the developing human fetus are unknown. For this reason and because molecular inhibitors of Wee1 kinase are known to be teratogenic, women of child-bearing potential (WoCBP) may be included only if acceptable contraception is in place for two weeks before study entry, for the duration of the treatment with the study drug, and for 2 months after the last dose of AZD1775. Male patients who are involved in the study must agree to avoid procreative and unprotected sex (i.e., by using acceptable forms of contraception) and must not donate sperm during the study and for 3 months after the last dose of AZD1775. Where the female partner is pregnant or not using effective birth control, men should be advised to abstain while in the study and for 3 months after the last dose of AZD1775. Female partners, who are of child-bearing potential, of men participating in clinical studies of AZD1775 will also be required to use effective contraceptive measures while their partner is on study drug and for 3 months thereafter. Male patients will be advised to arrange for the freezing of sperm samples prior to the start of the study should they wish to father children while on AZD1775 or during the 3 months after stopping AZD1775.
- **3.1.9** Because there is an unknown but potential risk for adverse events in nursing infants secondary to treatment of the mother with the study drugs, breastfeeding should be discontinued prior to the first of study drug and women should refrain from nursing throughout the treatment period and for 14 days following the last dose of study drug.
- **3.1.10** Patients must be able to swallow whole tablets or capsules. Nasogastric or G-tube administration is not allowed. Any gastrointestinal disease which would impair ability to swallow, retain, or absorb drug is not allowed.
- **3.1.11** Ability to understand and the willingness to sign a written informed consent document.

3.1.12 Patients with prostate cancer can continue to receive treatment with GnRH agonists while on study, as long as there is evidence of disease progression on therapy.

